9.3. Baseline examinations (FAS)

Table 10. DNA/antibody tests

Items	Indicator	Experimental group	Control group	Total
Blood EBV-DNA	Normal n (%)			
	Abnormal but not clinically significant n (%)			
	Abnormal and clinically significant n (%)			
	Not tested n (%)			
	Total (Missing)			
	Statistics			
	P-value			
Blood CMV antibody	Normal n (%)			
	Abnormal but not clinically significant n (%)			
	Abnormal and clinically significant n (%)			
	Not tested n (%)			
	Total (Missing)			
	Statistics			
	P-value			
IgM	Normal n (%)			
	Abnormal but not clinically significant n (%)			
	Abnormal and clinically significant n (%)			

IgG	Not tested n (%)			
	Total (Missing)			
	Statistics			
	P-value			
	Normal n (%)			
	Abnormal but not clinically significant n (%)			
	Abnormal and clinically significant n (%)			
	Not tested n (%)			
	Total (Missing)			
	Statistics			
	P-value			
<hr/>				
Table 11. Hepatitis virus				
Items	Indicator	Experimental group	Control group	Total
HBs-Ag	Normal n (%)			
	Abnormal but not clinically significant n (%)			
	Abnormal and clinically significant n (%)			
	Not tested n (%)			
	Total (Missing)			
	Statistics			
	P-value			
	Normal n (%)			
	Abnormal but not clinically significant n (%)			
	Abnormal and clinically significant n (%)			
Anti-HCV	Not tested n (%)			
	Total (Missing)			
	Statistics			
	P-value			
	Normal n (%)			
	Abnormal but not clinically significant n (%)			
	Abnormal and clinically significant n (%)			
	Not tested n (%)			
	Total (Missing)			
	Statistics			
	P-value			

Table 12. Examination of mycobacterium tuberculosis and fungi

Items	Indicator	Experimental group	Control group	Total
Mycobacterium tuberculosis test	Normal n (%)			
	Abnormal but not clinically significant n (%)			
	Abnormal and clinically significant n (%)			
	Not tested n (%)			
	Total (Missing)			
	Statistics			
	P-value			
Fungal examination	Fungal G test n (%)			
	Fungal other n (%)			
	Total (Missing)			
	Statistics			
	P-value			
Fungal examination result	Normal n (%)			
	Abnormal but not clinically significant n (%)			
	Abnormal and clinically significant n (%)			
	Not tested n (%)			
	Total (Missing)			
	Statistics			
	P-value			

Table 13. Urine test

Items	Indicator	Experimental group	Control group	Total
24hr urine protein (>3 years old)	Normal n (%)			
	Abnormal but not clinically significant n (%)			
	Abnormal and clinically significant n (%)			
	Not tested n (%)			
	Total (Missing)			

	Statistics
	P-value
Urine protein/serum creatinine	Normal n (%)
	Abnormal but not clinically significant n (%)
	Abnormal and clinically significant n (%)
	Not tested n (%)
	Total (Missing)
	Statistics
	P-value

Table 14. Glomerular filtration rate

Items	Indicator	Experimental group	Control group	Total
Examine or not	No n (%)			
	Yes n (%)			
	Total (Missing)			
	Statistics			
	P-value			
eGFR	Normal n (%)			
	Abnormal but not clinically significant n (%)			
	Abnormal and clinically significant n (%)			
	Not tested n (%)			
	Total (Missing)			
	Statistics			
	P-value			

Table 15. Retained biological samples of blood and urine

Items	Indicator	Experimental group	Control group	Total
Retained biological samples of blood and urine	No n (%)			
	Yes n (%)			

Total (Missing)

Statistics

P-value

Table 16. Chest X-ray

Items	Indicator	Experimental group	Control group	Total
Result				
	Normal n (%)			
	Abnormal but not clinically significant n (%)			
	Abnormal and clinically significant n (%)			
	Not tested n (%)			
	Total (Missing)			
	Statistics			
	P-value			

Table 17. ECG examinations

Items	Indicator	Experimental group	Control group	Total
Result				
	Normal n (%)			
	Abnormal but not clinically significant n (%)			
	Abnormal and clinically significant n (%)			
	Not tested n (%)			
	Total (Missing)			
	Statistics			
	P-value			

Table 18. Primary diagnosis

Items	Indicator	Experimental group	Control group	Total
Primary diagnosis	Steroid-sensitive nephrotic syndrome (SSNS) n (%)			
	Steroid-resistant nephrotic syndrome (SRNS) n (%)			
	Secondary nephrotic syndrome n (%)			

Steroid-dependent nephrotic syndrome (SDNS) n (%)
Frequently relapsing nephrotic syndrome (FRNS) n (%)
Other nephrotic syndrome n (%)
Total (Missing)
Statistics
P-value

9.4. Efficacy analysis (FAS/PPS)

9.4.1. Primary efficacy indicators: 1-year relapse-free survival rate

Table 19. 1-year relapse-free survival analysis

Items	Indicator	FAS		PPS	
		Experimental group	Control group	Experimental group	Control group
1-year recurrence time (days)	N (Missing)				
	Endpoint event (%)				
	Censoring (%)				
	Median survival time				
	95%CI				
	Q1, Q3				
	Log-rank test				
	P-value				
Cox regression analysis	Hazard Ratio				
	95%CI				
	Wald chi-square				
	P-value				

Note: The independent variables of Cox regression analysis are group and Site. Same below.

Figure 1. 1-year relapse-free survival analysis chart (FAS)

Figure 2. 1-year relapse-free survival analysis chart (PPS)

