3.2 To assess the safety outcomes of test drugs

Changes of vital signs (respiration and heart rate), routine blood and urine tests, liver function, renal function, blood glucose, ECG, chest X-ray, and observation of clinically reported adverse events and adverse reactions.

4. Study design

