4.5.3. Elimination criteria

- Those who fail to take the test drugs as required, with a compliance <80% or >120%.
- Those who cannot cooperate well or complete the follow-up as planned, and those who change the drug dose at will.

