7.1. Analysis data set

Full analysis set (FAS): It refers to the set of eligible cases and drop-off cases. The cases are required to have evaluation data after at least one treatment, but excluding the eliminated cases. Per-protocol set (PPS): It refers to the set of cases that meet the inclusion criteria, do not meet the exclusion criteria and complete the treatment plan, that is, the analysis of cases that meet the trial protocol, have good compliance and complete the specified content in CRF (PP analysis).

Safety set (SS): It refers to the actual data with safety index records after receipt of at least one treatment. The missed safety values shall not be carried forward. It includes some eliminated cases that can be evaluated, such as those whose age exceeds the inclusion criteria, but excludes those whose safety judgment cannot be made due to the use of banned drugs. For the incidence of adverse reactions, the number of cases in the safety set is used as the denominator.

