8.1.6. Safety analysis

Safety analysis mainly adopts safety set. All adverse events are coded by MedDRA 20.0 to describe the total number and incidence of adverse events (including serious adverse events), and the

frequency table is used to describe the frequency, severity of each adverse event and its relationship with the treatment. Adverse events relevant (related, probably related, and possibly related) to this research treatment are described and listed separately. Other safety indicators will also be described and summarized. The laboratory changes with clinical significance will be counted as AE.

9. Statistical analysis results

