9.1. Research overview

Table 1. Distribution of subjects at each site (All enrolled subjects)

Research Site	Group	No. of subjects enrolled	No. of subjects drop-out	Drop-out rate	No. of subjects eliminated	Elimination rate	No. of subjects completed
Site 1	Experimental group						
	Control group						
	Total						
Site 2	Experimental group						
	Control group						
	Total						
...							
Total	Experimental group						
	Control group						
	Total						

Note: 1. The Site name is not displayed in following table, only the site number. Same below. 2. No. of subjects completed = No. of subjects enrolled - No. of subjects drop-out. Elimination refers to subjects who complete the trial, but were not included in the PPS. Subjects who withdrew due to the endpoint event were considered to have completed the trial. 3. Drop-out rate = No. of subjects drop-out / No. of subjects enrolled; Elimination rate = No. of subjects eliminated / No. of subjects enrolled.

Table 2. Distribution of subjects at each site

Site	PPS			FAS			SS		
	Experimental group	Control group	Total	Experimental group	Control group	Total	Experimental group	Control group	Total
Site 1									
Site 2									
Total									

Table 3. Trial completion and distribution of analysis data set (All enrolled subjects)

Items	Indicator	Experimental group	Control group	Total
No. of subjects enrolled	Yes			
	No			
Complete 1 week follow-up	Yes			
	No			
Complete 4 week follow-up	Yes			
	No			
Complete 8 week follow-up	Yes			
	No			
Complete 16 week follow-up	Yes			
	No			
Complete 24 week follow-up	Yes			
	No			
Complete 32 week follow-up	Yes			
	No			
Complete 40 week follow-up	Yes			
	No			
Complete 52 week follow-up	Yes			
	No			
Trial completion	Yes			

Items	Indicator	Experimental group	Control group	Total
	No			
Treatment discontinuation reason	Subject voluntarily withdrew prematurely			
	Decision by the investigator			
	Poor compliance that decided by the investigator			
	Meet the exclusion criteria, or did not meet the inclusion criteria			
	Refusal to continue trial participation			
	Lack of efficacy			
	Adverse events			
	Lost to follow-up			
	Death			
	Other			
FAS				
PPS				
SS				

Note: Follow-up time (years) = (last visit date - random date + 1) / 365.25. Complete 1 week follow-up: follow-up duration \geq 1 week, and so on.

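### The by-visit laboratory comparisons between arms run only on the FAS and PPS, so eliminated children whom the safety set keeps are missing from them

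*SAP*

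**What the plan says.** SAP 3.2 includes "routine blood and urine tests, liver function, renal function, blood glucose" among the safety outcomes. SAP 8.1.6 states: "Safety analysis mainly adopts safety set".

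The between-arm laboratory tables by visit are nevertheless in section 9.4, headed "Efficacy analysis (FAS/PPS". Table 23 (eGFR) has FAS and PPS columns only, with between-arm statistics and P-values at each listed visit. A note under Table 24 carries that layout forward. Under the same heading come Tables 24-27 (other renal measures), 41-50 (liver function and glucose), 51-54 (blood routine) and 55-58 (urine routine).

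SAP 7.1 defines the FAS as including drop-outs, "but excluding the eliminated cases". The PPS requires good compliance. The safety set retains "some eliminated cases that can be evaluated". SAP 4.5.3 eliminates children "with a compliance <80% or >120" percent, and also those who cooperate poorly, do not complete follow-up or change the dose themselves. The note to Table 1 gives a narrower meaning: "Elimination refers to subjects who complete the trial, but were not included in the PPS".

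**The concern.** These tables would show when creatinine, ALT, glucose or white cells move during treatment and whether the arms differ. Leaving out poorly compliant children applies a post-randomisation exclusion to a safety comparison, and compliance can be related to tolerability. The SAP's own safety population would have kept those who can be evaluated.

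The interim visits matter because target exposure is highest in the first six months (SAP 5.2.1). The tacrolimus trough target is 5-10 ng/mL and then below 5. The MPA-AUC target is 30-50 µg·h/mL and then at most 40. Day 364, the only post-baseline time point in the safety set's laboratory summary and shift tables, falls in the lower-exposure period. The dose-reduction and withdrawal rules (SAP 4.5.4, 5.2.3, 5.2.4) act on creatinine, leukocytes and ALT or bilirubin during treatment.

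**Working it through.** **Who is in each set**

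| Set (SAP 7.1) | Eliminated children |
|---|---|
| FAS | Excluded by definition |
| PPS | Excluded through the compliance and completion requirements |
| Safety set | Kept in part, where they can be evaluated |

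Elimination has two readings. On the Table 1 note, eliminated children completed the trial but are outside the PPS. The FAS is then the PPS plus the drop-outs, and eliminated children are in neither set. On SAP 4.5.3, incomplete follow-up also counts as elimination, which blurs the boundary with drop-out. Whoever is classed as eliminated is still outside both sets.

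**What is tabulated on FAS/PPS**

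- Tables: 23-27 = 5 and 41-58 = 18, so 5 + 18 = 23.
- Post-baseline visits in the Table 23 shell: 2, 4, 5, 6, 7, 8 and 9 = 7. Visit 3 is not in the shell.
- Table-visits with between-arm statistics: 23 × 7 = 161.
- At Days 7, 56, 112, 168, 224 and 280: 23 × 6 = 138.

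**What the safety set has (SAP 9.5 and attachments)**

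- Tables 62-66: adverse events with P-values. Laboratory changes judged clinically significant enter here.
- Tables 69-70: WBC and lymphocyte categories compared between arms at Visits 1 and 9, giving 2 post-baseline comparisons.
- Tables 71-104: shift tables from baseline to Day 364 by arm, with no between-arm test in the shell.
- Tables 121-125: subject listings of normal-to-abnormal results, with no summary by arm.
- Tables 67-68: heart rate and respiratory rate compared by visit. These are vital signs, not laboratory values.

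Between-arm comparisons of laboratory values on the safety set at Day 7-280: 0.

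**Illustration of scale (assumed inputs)**

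The documents give no elimination rate. Suppose a fraction e of an arm is eliminated and, for simplicity, that the safety set equals the FAS plus all eliminated children. With mean change mF in the FAS and mE in the eliminated:

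- Safety-set mean = (1 − e) × mF + e × mE
- FAS mean − safety-set mean = e × (mF − mE)

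Take e = 0.05 to 0.15, that is 135 × 0.05 = 6.75 to 135 × 0.15 = 20.25, or about 7 to 20 children per arm. Take an eGFR gap of 10 to 20 mL/min/1.73m².

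- Low end: 0.05 × 10 = 0.5
- High end: 0.15 × 20 = 3.0

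That arm's mean would shift by 0.5 to 3.0 mL/min/1.73m², in either direction. If elimination is alike in both arms, the between-arm difference is unchanged.

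**The case against.** The strongest reply is that laboratory safety is already covered on the safety set. SAP 8.1.6 says "The laboratory changes with clinical significance will be counted as AE", so a laboratory abnormality arising at Day 7-280 can reach the between-arm adverse-event tables. Shift tables and listings add to this, and 8.1.6 does not promise by-visit laboratory testing on the safety set. This stands as a limit on the point: the plan is not without laboratory safety output. But adverse-event coding depends on a judgement of clinical significance and does not show how mean values move over time. The plan already does this by visit on the safety set for heart rate and respiration and gives no reason to treat ALT or WBC differently.

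It can also be said that the clearest toxicity cases stay in the FAS. Confirmed creatinine doubling with eGFR below 60, unresolved liver abnormality and unacceptable adverse events require withdrawal (SAP 4.5.4). Those children become drop-outs, whom the FAS keeps. Dose cuts directed by the protocol need not count as poor adherence. This is fair and reduces the likely bias. It does not cover children who take too little or too much drug without meeting a withdrawal rule.

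On the counts, seven of the 18 tables (41, 43, 44 and 46-49) concern analytes outside the flow chart's definition of liver function. They supply 7 × 7 = 49 of the 161 table-visits, so without them 112 remain. Haemoglobin and albumin (Tables 37-38) could equally be added, giving 25 × 7 = 175. The scope can be argued either way, but the gap is the same. Tables 41-58 are printed as titles only, so their population is inferred from the section heading and the carried-forward layout. A few other tables in 9.4 (28, 29, 34 and 61) show no FAS/PPS columns.

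Finally, the cause is the FAS definition itself. Correcting it would largely remove this problem, but as written the plan still needs the table change.

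**Conclusion.** The point holds and is minor. Under the SAP as written, 23 by-visit laboratory tables (161 table-visits, 138 of them at Day 7-280) exclude eliminated children, and the safety set has no between-arm comparison of laboratory values before Day 364. It is strongest for Tables 41-58: apart from urine protein (Table 58), which is close to the efficacy measures, their analytes are not named as secondary efficacy outcomes in SAP 3.1. For Tables 23-27 the FAS/PPS columns are proper, because renal function is also a secondary efficacy outcome (SAP 6.2.2), and only a safety-set version is missing.

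The conclusion about populations rests on the 9.4 heading, the carried-forward layout and the SAP 7.1 definitions. Any bias depends on how many children are eliminated, how they differ and whether the arms differ in this, none of which the documents give. The 0.5 to 3.0 mL/min/1.73m² range is an illustration on assumed inputs. The primary result and the planned adverse-event comparison are not affected.

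**What to change.** - Produce Tables 41-58 on the safety set in section 9.5, using the Table 67 shell. Table 58 can keep an FAS/PPS version as well.
- Add a safety-set version of Tables 23-27 and keep their FAS/PPS columns. The same can be done for Tables 37-38.
- State in SAP 8.1.6 that laboratory safety conclusions rest on the safety-set versions.

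The cost is a population flag on table programs already planned and a line of SAP wording. The flow chart schedules these tests at every visit from Visit 2 to Visit 9, so no new data are needed. On the Table 1 reading the eliminated children completed the trial, and their interim values should exist.

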Medical history (course of disease, frequency of relapses in 1 year and 6 months before enrollment, steroid dosage)	√									
Vital signs	√	√	√	√	√	√	√	√	√	√

Items	Screening and enrollment period		Treatment and follow-up period							
	Screen (V0)	Visit 1 (V1)	Visit 2 (V2)	Visit 3 (V3)	Visit 4 (V4)	Visit 5 (V5)	Visit 6 (V6)	Visit 7 (V7)	Visit 8 (V8)	Visit 9 (V9)
Height and weight	√	√	√	√	√	√	√	√	√	√
Physical examination	√	⊙	√	√	√	√	√	√	√	√
Blood routine examination	√	⊙	√	√	√	√	√	√	√	√
Urine routine examination	√	⊙	√	√	√	√	√	√	√	√
Fasting blood glucose	√		√	√	√	√	√	√	√	√
Serum liver function	√	⊙	√	√	√	√	√	√	√	√
Blood lipid	√	⊙	√	√	√	√	√	√	√	√
Serum renal function	√	⊙	√	√	√	√	√	√	√	√
Blood EBV-DNA, and CMV antibody	√									√
24h urinary protein (>3 years old)	√	⊙	√	√	√	√	√	√	√	√
Urinary protein / creatinine	√	⊙	√	√	√	√	√	√	√	√
eGFR	√	⊙	√	√	√	√	√	√	√	√

Items	Screening and enrollment period		Treatment and follow-up period							
	Screen (V0)	Visit 1 (V1)	Visit 2 (V2)	Visit 3 (V3)	Visit 4 (V4)	Visit 5 (V5)	Visit 6 (V6)	Visit 7 (V7)	Visit 8 (V8)	Visit 9 (V9)
Tacrolimus concentration in plasma			√	√	√	√	√	√		√
Mycophenolic acid concentration in plasma			√				√			
Chest X-ray	√									√
ECG	√									√
Markers of hepatitis B and hepatitis C virus	√									
Examination of Mycobacterium tuberculosis and fungi	√									
Biological samples of blood and urine	√						√			√
Drug distribution and measurement		√	√	√	√	√	√	√	√	√
Guidance on the administration of test drug		√	√	√	√	√	√	√	√	√

Items	Screening and enrollment period		Treatment and follow-up period							
	Screen (V0)	Visit 1 (V1)	Visit 2 (V2)	Visit 3 (V3)	Visit 4 (V4)	Visit 5 (V5)	Visit 6 (V6)	Visit 7 (V7)	Visit 8 (V8)	Visit 9 (V9)
Clinical efficacy (relapse or no)			√	√	√	√	√	√	√	√
Concomitant medication	√	√	√	√	√	√	√	√	√	√
Adverse event			√	√	√	√	√	√	√	√
Record case report form	√	√	√	√	√	√	√	√	√	√

Remarks:

1. Liver function: ALT, TBiL, ALB; Renal function: creatinine, urea nitrogen, uric acid, Cystatin C;
2. Blood lipids: Triglycerides, cholesterol; Urinary protein / creatinine: morning urine; Markers of hepatitis B and hepatitis C virus: HBsAg, HBeAg, HBcAb, HCV;
3. Mycobacterium tuberculosis examination: T-sport; Fungal examination: fungal G test or other; Estimated glomerular filtration rate: $eGFR = K \times \text{height (cm)} / \text{serum creatinine (mg / dL)}$ (see Appendix);
4. Visit time window: ± 3 days for visit 2, and ± 7 days for other visits;

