8.1.3. Primary efficacy analysis

Logrank test is used for the analysis of relapse-free survival rate which is then used as a covariate for stratification by Sites. HR and its 95% confidence interval (CI) are calculated with Cox proportional hazard model to estimate the efficacy, the confidence interval is applied to verify the superiority of the experimental group and the control group, with a cut-off value of 1 (risk ratio). The model incorporates the same covariate as the Logrank test for fitting, and the definition method of covariates is also the same as that in the Logrank test. The Kaplan-Meier curve of relapse-free survival is drawn by treatment groups. The 1-year relapse-free survival rate and its confidence interval are then calculated.

Calculation rules for the main efficacy indicators:

- If relapse occurred within 9 visits (within 364 ± 7 days) or unscheduled visits within 365 days of randomization, defined as the occurrence of endpoint events. Time of relapse = date of relapse - Random date + 1, calculated by days.
- If the visit stipulated in the protocol was not completed within 9 visits (within 364 ± 7 days) due to loss of follow-up midway or withdrawal or other reasons, it is defined as censoring. Time of

censoring = date of withdrawal - random date + 1, calculated by days.

- If the visit stipulated in the protocol was not completed within 9 visits (within 364 ± 7 days) due to death in the trial, it is defined as censoring. Time of censoring = Death date - random date + 1, calculated by days.
- If the visit stipulated in the protocol was completed and there is no relapse within 9 visits (within 364 ± 7 days), it is defined as censoring. Time of censoring = date of visit 9 (within 364 ± 7 days) - random date + 1, calculated by days.

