	P-value			
	No n (%)			
	Yes n (%)			
	Total (Missing)			
	Statistics			
	P-value			
Feeding	Mixed feeding n (%)			
	Single feeding n (%)			
	Total (Missing)			
	Statistics			
	P-value			
Partial eclipse	No n (%)			
	Yes n (%)			
	Total (Missing)			
	Statistics			
	P-value			
History of growth and development	Normal n (%)			
	Abnormal n (%)			
	Total (Missing)			
	Statistics			
	P-value			
Vaccination history	No n (%)			
	Yes n (%)			
	Total (Missing)			

Items	Indicator	Experimental group	Control group	Total
	Statistics			
	P-value			

Table 7. History of other diseases, concomitant medications and nephrotic syndrome

Items	Indicator	Experimental group	Control group	Total
History of other diseases and concomitant medications	No n (%)			
	Yes n (%)			
	Total (Missing)			
	Statistics			
	P-value			
History of nephrotic syndrome (years)	N (Missing)			
	Mean (SD)			
	Median			
	Q1, Q3			
	Min, Max			
	Statistics			
	P-value			
History of nephrotic syndrome (Number of relapses in the past 1 year)	N (Missing)			
	Mean (SD)			
	Median			
	Q1, Q3			
	Min, Max			
	Statistics			
	P-value			
History of nephrotic syndrome (Number of relapses in the past 6 months)	N (Missing)			
	Mean (SD)			
	Median			
	Q1, Q3			

Items	Indicator	Experimental group	Control group	Total
	Min, Max			
	Statistics			
	P-value			

Note: History of other diseases and concomitant medications: history of diseases other than the nephrotic syndrome, such as pneumonia, cardiovascular, diabetes, purpura and enuresis, etc.

Table 8. Visual palpation of physical examination Items

Items	Indicator	Experimental group	Control group	Total
Heart	Normal n (%)			
	Abnormal but not clinically significant n (%)			
	Abnormal and clinically significant n (%)			
	Not tested n (%)			
	Total (Missing)			
	Statistics			
	P-value			
Superficial lymph node	Normal n (%)			
	Abnormal but not clinically significant n (%)			
	Abnormal and clinically significant n (%)			
	Not tested n (%)			
	Total (Missing)			
	Statistics			
	P-value			
Skin and sclera	Normal n (%)			
	Abnormal but not clinically significant n (%)			
	Abnormal and clinically significant n (%)			
	Not tested n (%)			
	Total (Missing)			
	Statistics			
	P-value			

Thyroid gland	Normal n (%)
	Abnormal but not clinically significant n (%)
	Abnormal and clinically significant n (%)
	Not tested n (%)
	Total (Missing)
	Statistics
	P-value
	Normal n (%)
	Abnormal but not clinically significant n (%)
	Abnormal and clinically significant n (%)

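### The primary Cox model adjusts only for group and site; adding prior-year relapse count and steroid dependence, if they are prognostic, could recover some power at almost no cost

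*SAP*

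**What the plan says.** **Primary model.** SAP 8.1.3 says "Logrank test is used for the analysis of relapse-free survival rate which is then used as a covariate for stratification by Sites", and of the Cox model, "The model incorporates the same covariate as the Logrank test for fitting". Protocol 11.3.3 has the same rule, with centres in place of sites. The note under SAP Table 19 (9.4.1) closes the list: "The independent variables of Cox regression analysis are group and Site". Both documents judge superiority by the Cox confidence interval against a cut-off of 1. Table 19 also reports a separate log-rank P-value.

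**Baseline data.** The flow chart (protocol 1.3) schedules medical history at screening, including "frequency of relapses in 1 year and 6 months before enrollment, steroid dosage". Frequent relapse or steroid dependence is the first inclusion criterion (protocol 4.1).

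**Use of those data.** The relapse count appears in SAP Table 7 ("Number of relapses in the past 1 year") and dependence in SAP Table 18 ("Steroid-dependent nephrotic syndrome (SDNS) n"), each with a between-group P-value. Neither variable enters any efficacy or sensitivity model.

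**Randomisation.** Protocol 3.3.1 and SAP 4.2.1 describe 1:1 allocation by sequential envelopes. They name no stratification on either variable.

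**The concern.** The endpoint is the next relapse, and the two unused variables describe each child's relapse history and steroid dependence. They are the obvious candidates for prediction among the data already planned. In a Cox model, omitting a covariate that is truly prognostic pulls the treatment HR towards 1, even with perfect balance between arms, and lowers power. Because allocation is not described as stratified on these variables, a chance imbalance would also go unadjusted.

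The SAP tests balance on both variables but does not say what follows if they differ. In an open-label trial whose SAP (4.1) describes enrolment as completed, that leaves room for an adjustment chosen after the fact. Naming the covariates beforehand closes that gap.

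**Working it through.** **1. Reproduce the plan's calculation** (protocol 3.3.2 and Appendix 4: one-year relapse-free survival 0.56 and 0.70, 114 and 115 children, accrual 2 of 3 years, no loss, two-sided 0.05).

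- Hazards, −ln S(1): 0.5798 (MMF) and 0.3567 (FK506). HR = 0.3567/0.5798 = 0.6151, as stated.
- Probability of relapse with uniform entry: 1 − (e^(−λ) − e^(−3λ))/(2λ).
  - MMF: 1 − (0.5600 − 0.1756)/1.1596 = 0.6685; × 114 = 76.2 events.
  - FK506: 1 − (0.7000 − 0.3430)/0.7133 = 0.4995; × 115 = 57.4 events.
- Total 133.7 before rounding (plan: 133.8).
- Schoenfeld power: Φ(√(133.7/4) × 0.4859 − 1.96) = Φ(0.849) = 0.802 (plan: 0.8009).
- 229/0.85 = 269.4, rounded up to 270.

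The plan's figure reproduces. It assumes no covariate adjustment.

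**2. Events under the analysis as written.** Protocol 3.2 sets a one-year observation period, and SAP 8.1.3 censors at Visit 9. With 15% loss over the year, the loss rate is θ = −ln 0.85 = 0.1625 and the event probability is λ/(λ+θ) × (1 − e^(−(λ+θ))).

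- MMF: 0.7811 × 0.524 = 0.4093; × 135 = 55.3.
- FK506: 0.6870 × 0.405 = 0.2782; × 135 = 37.6.
- Total about 92.8. Power = Φ(√(92.8/4) × 0.4859 − 1.96) = Φ(0.381) = 0.648.

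**3. Effect of adding the covariates.** This used 4,000 simulated trials per setting, with 270 children, 12 sites (the number in SAP 4.1), one-year follow-up and 15% loss. Arm hazards were calibrated so that the marginal one-year rates stay at 0.56 and 0.70. The test is the Cox Wald test with group and site indicators, without and then with the two covariates. Assumed, because the documents do not say: normally distributed relapse count, 50% steroid dependent, independent covariates, no site effect, and every prognostic HR below.

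| HR per SD of count / HR for dependence | Power without | Power with | Gain (points) | Average HR without → with |
|---|---|---|---|---|
| 1.0 / 1.0 | 63.5% | 63.3% | −0.2 | 0.605 → 0.603 |
| 1.2 / 1.25 | 64.1% | 64.9% | +0.7 | 0.606 → 0.601 |
| 1.3 / 1.5 | 63.6% | 64.8% | +1.2 | 0.603 → 0.594 |
| 1.5 / 1.5 | 64.9% | 67.7% | +2.8 | 0.599 → 0.584 |
| 1.5 / 2.0 | 63.3% | 68.4% | +5.2 | 0.604 → 0.583 |
| 2.0 / 2.0 | 64.4% | 75.0% | +10.6 | 0.602 → 0.557 |

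Gains come from unrounded powers. The Monte Carlo standard error of one power is about √(0.64 × 0.36/4000) = 0.8 point. Both models were fitted to the same simulated trials, so the gains are more precise than that.

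**4. Two checks.** With the plan's own 2/3-year timing (229 children, about 131 to 134 events), the first four settings gain 0, 1.6, 2.8 and 5.8 points. A separate simulation (5,000 trials, 12 unequal sites, one standardised covariate) compared a site-stratified log-rank test with a site-stratified Cox model. Power went from 60.9% to 61.6% at a prognostic HR of 1.25 per SD, from 63.4% to 65.2% at 1.5, and from 63.1% to 70.8% at 2.0. Direction and range agree.

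**The case against.** The strongest reply is that this is a matter of efficiency, not an error. Under randomisation the site-only analysis is valid, and chance imbalance does not inflate type I error. That stands. A reader might infer that unstratified allocation makes the site-only result biased; the documents do not support that.

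The remaining objections limit the point or shape its remedy:

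- **Power is certainly lost.** A reader might infer this, but neither document gives a prognostic effect for either variable. Entry already restricts the trial to frequently relapsing or steroid-dependent children, which narrows the range of both. The loss could be near zero.
- **Every child has both values.** Collection is planned, but Tables 7 and 18 both allow for missing values. Table 18 lists SDNS and FRNS as separate rows under one total, so a child meeting both definitions has no clear code. FRNS can be met within six months of onset (protocol 4.6.4), so a past-year count may cover less than a year of disease. SAP section 8 fills in no missing data, so a covariate model could drop children.
- **Changing the Cox model changes the primary test.** Protocol 3.3.1 and SAP 4.2.1 name the log-rank test as the comparison. Its P-value would not move, and the same-covariate rule would be broken unless it is rewritten.
- **The simulation is simplified.** It treats the covariates as independent, although SDNS is itself defined by relapses (protocol 4.6.3), and it enters site as indicators rather than strata.
- **Adjustment would repair the power.** It would not. Power is near 64% mainly because one-year follow-up yields about 93 events against the 133.8 planned, which is a separate matter.

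**Conclusion.** The point holds as a recommendation. The model that carries the superiority decision leaves out two natural predictors that are planned to be collected for every child. Under one-year follow-up, adding them changes power by about 0 to 3 points if they are null to modest predictors and by 5 to 11 points if they are strong. If they carry no information, the change is −0.2 point, within simulation error. So little is risked for a possible gain.

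The size rests on assumed prognostic strengths and on the other simulation assumptions listed above. The gain bears on the conclusion only if the adjusted Cox result governs.

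**What to change.** Before outcome data are reviewed, amend SAP 8.1.3, the Table 19 note and protocol 11.3.3 as follows:

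1. Fit the Cox model for the HR and superiority interval with group, number of relapses in the past year (continuous) and SDNS (yes/no), stratified by site.
2. Code a child who meets both the SDNS and FRNS definitions as SDNS yes, and state how the count is taken when the disease has lasted less than a year.
3. Give a simple rule for missing covariates so that no child is dropped, for example replacing a missing count by the median over both arms and stating a fixed code for missing SDNS status.
4. Remove the requirement that the Cox covariates equal those of the log-rank test.
5. State whether the adjusted Cox result or the site-stratified log-rank test governs the conclusion.
6. Keep the site-only Cox model as a sensitivity analysis.

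**Cost.** No new data are needed. The change touches both documents, and protocol 12.1 sends protocol revisions made during the trial to the Ethics Committee. The HR becomes conditional on the covariates, and the report should say so.
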